## 2.0 PKG System

### PKG Watch

The PKG Watch is a wrist worn medical device that looks like a wristwatch. It is worn on the wrist of the most severely affected side and contains a rechargeable battery, a triaxial accelerometer, memory, an optional vibration and indicator light-based reminder to the subject when PD medications are due and a means for recording when Parkinson's disease (PD) medications were taken, as well as a capacitive sensor to detect removal from the wrist.

Subjects wear the device for 6-10 consecutive days. During this wear time the PKG Watch automatically collects data on the type of movement experienced by the patient 24 hours per day, can remind the patient to register when they have taken their PD medication as prescribed by their clinician, and the patient can indicate when he/she has taken each prescribed dose of PD medication.

At the end of the recording period, data are downloaded and analyzed using a proprietary algorithm to translate raw movement data collected by the PKG Watch into a multi-page, printable output of the patient's movement over the wear period. This output is called a "PKG." The maximum acceleration in each 2-minute epoch is identified and the mean spectral power surrounding this peak is calculated. Algorithms produce Bradykinesia Scores (BKS) and Dyskinesia Scores (DKS) every two minutes. The PKG includes:

- a scaled record of a dyskinesia score (DKS) representative of dyskinesia plotted against time of day for individual days over the full recording period (Figure 2).
- a scaled record of a bradykinesia score (BKS) representative of bradykinesia plotted against time of day for individual days over the full recording period (Figure 2).
- a record of periods of immobility, which may be indicative of periods of daytime sleep and somnolence, plotted against time of day.

- a record of periods when the patient was not wearing the PKG Watch or when it was 'off-wrist'.
- a record of the patient's self-reported compliance with their prescribed program of Parkinson's disease medication.
- a record of periods of tremor for each day and a tremor summary.

Dyskinesia + Bradykinesia Daytime Session Averages

[figure not shown]

Figure 1: PKG Main Plot

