2.1 Clinical Interpretation

Bradykinesia Scores (BKS) and Dyskinesia Scores (DKS) are continuous variables. In the case of the BKS, the scores can range from movements that are made with normal acceleration to those that have very low or no acceleration. There is a correlation between the median BKS and DKS between 0900-1800 hour and clinical rating scales.

A very high bradykinesia score represents complete immobility of the logger for that 2-minute period. These periods of immobility had a 85.2% concordance with the detection of sleep by ambulatory daytime polysomnography, ( $p < 0.0001$  Chi Squared). High Epworth Sleepiness Scores (ESS) were associated with a high proportion of time immobile (PTI) throughout the day ( $p > 0.01$  Mann-Whitney). The median PTI between 0900 -1800 hours in 30 age matched control subjects was 2%, representing 10 min. PD patients had higher PTI (median 4.8%) than controls ( $p < 0.0001$ , Mann-Whitney). PD subjects with a PTI above the 75th percentile (5% or 27 min) of controls had more bradykinesia, less dyskinesia and higher PDQ-39 scores than those with PTI below this level. There was no relationship between PTI and dose or type of PD

medications. However, in 53% of subjects, PTI increased in the 30-60 min after levodopa confirming that in some subject's levodopa results in increased sleepiness.

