3.1. Primary Objective

This is a randomized controlled trial (RCT) to evaluate treating uncontrolled patients with Parkinson’s Disease (PwP) to a target range established by published expert opinion. The study aims to evaluate clinical patient outcomes, quality of life measures and health care utilization of those patients specifically treated to a target range when using the PKG data in the clinical management of Parkinson’s disease (PD) in routine clinical care (treatment group) compared to those managed with medical history and clinical evaluation alone (control group) performed by a neurologist experienced in PD management. Both groups will be recommended to undergo medication changes until they reach a “controlled state” that is determined by either the clinician using standard of

care (SOC) (PKG- Group) or using PKG based targets and SOC assessments (PKG+ Group). For subjects in the treatment arm (PKG+ Group) the references will be according to the following table for purposes of analysis using PKG scores. Subjects will either be considered bradykinetic (BKS scores exceed targets; BKS >25) or Dyskinetic (DKS scores exceed targets; DKS >9):

	Target Range
Bradykinesia Score (BKS)	Median BKS 23-25
Dyskinesia Score (DKS)	Median DKS 7-9

The main objective of this study is to evaluate whether PwP who are managed with the aid of objective measurement and use of target ranges have improved PD symptoms and outcomes as compared to individuals treated using only standard of care (medical history, neurological examination).

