3.4. Secondary Endpoints

The following secondary clinical outcomes will be measured at and compared between baseline and 4 months follow-up visits.

Secondary clinical outcomes will include:

- 1. Percent “responders” for MDS-UPDRS Total score (based on a minimum clinically important change of >4 points)**

This is a comparison of the percent responders for the within-group change from baseline to 4 months for PKG+ and PKG- groups. This is a comparison of the percent responders for the within-subject change from baseline to 4 months for PKG+ and PKG- groups.

2. Change in motor endpoints from baseline to 4 months including:

a. MDS-UPDRS Part III

- i. Within-subject changes will be calculated as visit value minus baseline value such that a negative change reflects an improvement and positive change signifies a deterioration. Summaries of improved/same/worsened will be provided along with the continuous summaries. (example, 35 (4-month) – 45 (BL))

b. PKG Bradykinesia score (BKS),

- i. Within-subject changes will be calculated as visit value minus baseline value such that a negative change reflects an improvement and positive change signifies a deterioration. Summaries of improved/same/worsened will be provided along with the continuous summaries. (example, 25 (4-month) – 30 (BL))

c. PKG Dyskinesia score (DKS) and measurement of OFF time

- i. Within-subject changes will be calculated as visit value minus baseline value such that a negative change reflects an improvement and positive change signifies a deterioration. Summaries of improved/same/worsened will be provided along with the continuous summaries. (example, 5 (4-month) – 9 (BL))
- ii. Measurement of OFF time will not be included in this analysis

3. Change in PDQ-39 from baseline to 4 months

Change in PDQ-39 from baseline to 4-months. Tabulate values and proportions and changes from baseline to each visit.

Within-subject changes will be calculated as visit value minus baseline value such that a negative change reflects an improvement and positive change signifies a deterioration. Summaries of improved/same/worsened will be provided along with the continuous summaries.

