The Parkinson's Disease Questionnaire will be completed by the patient at baseline, 4 months and annual follow-up visits concerning activities in the last month including self-care, walking ability, falling, mental stability, somnolence, etc. This a 5-point scale (never, occasionally, sometimes, often, always). A dimension score is calculated for each of 8 sections and a summary index is then calculated for the entire assessment.

4. Change in MDS-UPDRS Part I from baseline to 4 months

Change in MDS-UPDRS Part I and subsections as noted on the MDS-UPDRS data collection from baseline to 4 months.

Within-subject changes will be calculated as visit value minus baseline value such that a negative change reflects an improvement and positive change signifies a deterioration. Summaries of improved/same/worsened will be provided along with the continuous summaries.

5. Change in MDS-UPDRS Part II from baseline to 4 months

Change in MDS-UPDRS Part II and subsections as noted on the MDS-UPDRS data collection from baseline to 4 months.

Within-subject changes will be calculated as visit value minus baseline value such that a negative change reflects an improvement and positive change signifies a deterioration. Summaries of improved/same/worsened will be provided along with the continuous summaries.

6. Change in MDS-UPDRS Part IV from baseline to 4 months

Change in MDS-UPDRS Part IV and subsections as noted on the MDS-UPDRS data collection from baseline to 4 months.

Within-subject changes will be calculated as visit value minus baseline value such that a negative change reflects an improvement and positive change signifies a deterioration. Summaries of improved/same/worsened will be provided along with the continuous summaries.

7. Change in PKG Scores including BKS, DKS, PTT, FDS and PTI from baseline to 4 months

Change in PKG scores from baseline to interim1, interim 1 to interim2, interim 2 to interim3, interim3 to 4 months for those with interim visits conducted (uncontrolled) or baseline to 4 months for controlled.

Within-subject changes will be calculated as visit value minus baseline value such that a negative change reflects an improvement and positive change signifies a deterioration. Summaries of improved/same/worsened will be provided along with the continuous summaries.

PKG summary scores will be reported on the PKG at baseline, interims (if applicable for those uncontrolled), and 4 months including the following:

- Bradykinesia Score

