- Dyskinesia Score
- Fluctuation Score
- Percent Time Immobile (PTI)
- Percent Time Tremor Present (PTT)

Evaluation of individual patient and subgroup response from baseline assessed by change in PKG BK or DK scores from baseline to 4 months for controlled (in target range) and uncontrolled (out of target range) in PKG+ and PKG- groups

- Rate of subjects who were uncontrolled at baseline (PKG Summary Scores exceeded targets) and then became controlled at the 4-month visit (PKG Summary Scores reduced to below targets).
- Rate of subjects unresponsive to medication changes (i.e. no change to PKG BK scores with LED increase)
- Rate of subjects who required treatment changes but were unwilling to make changes (this group may not show any impacts to outcomes)
- Rate of subjects who required treatment changes but were contraindicated to make changes (this group may not show any impacts on outcomes)

8. Change in LED from baseline to each interim visit and 4 months

Calculation of Levodopa Equivalent Dose (LED) at each visit for each patient and a comparison of change in LED at each visit for each patient. If a change is made at the scheduled visit, the change is calculated for the next visit (e.g., a change at the BL visit means the subject has started taking the new medication/dose/frequency change the day after the BL visit, etc.) – See Appendix for reference in calculating LED.

Rate and change in PD medications including medication type, dosing, increase, decrease from baseline to interim1, interim2, interim3, and 4 months.

An analysis to look at medication change amount and frequency and impact on outcome of MDS-UPDRS and PKG BKS will be performed. Patients will be ranked by amount of LED change at each visit and grouped by number of times they had medication changes at a visit (e.g. 0, 1, 2 times, etc.) from baseline to the 4 month visit and correlated to the outcome of MDS-UPDRS and PKG score of BKS at 4 months.

- Rate of subjects who were marked as uncontrolled but had no medication changes will be noted.
- Rate of subjects who had medication changes but were less than 100mg LED will be noted.

9. PKG Patient Survey at 4 months

PKG Patient Survey at 4 months. Tabulate values and proportions and changes from baseline to each visit.

The rate at 4 months will be calculated for the PKG+ and PKG- groups for each section of the survey.

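### The SAP's rate of subjects unresponsive to medication changes counts only unchanged BKS after an LED increase, so it leaves out subjects whose BKS worsened

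*SAP*

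**What the plan says.** SAP 3.4 item 7 covers change in the PKG scores. It includes an evaluation of individual and subgroup response, "assessed by change in PKG BK or DK scores from baseline to 4 months", for subjects in and out of target range in both arms. Four rates are listed under it. The second is "Rate of subjects unresponsive to medication changes (i.e. no change to PKG BK scores with LED increase". The bracket works as the definition. It gives no tolerance around zero, no direction of change and no minimum LED increase.

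The same item fixes the direction of BKS change (4-month value minus baseline): a "negative change reflects an improvement and positive change signifies a deterioration". It adds that "Summaries of improved/same/worsened will be provided along with the continuous summaries", with no numeric limits for the middle category.

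On the nature of the score, Protocol 2.1 states that "Bradykinesia Scores (BKS) and Dyskinesia Scores (DKS) are continuous variables", and the Protocol's PKG Watch section says that "Algorithms produce Bradykinesia Scores (BKS) and Dyskinesia Scores (DKS) every two minutes". The target in SAP 3.1 is written in whole points, "Median BKS 23-25", and a subject counts as bradykinetic when BKS is above 25. Neither document states the precision to which the median BKS is reported.

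Elsewhere the SAP does set limits. MDS-UPDRS responders need a "minimum clinically important change of >4 points", and item 8 uses 100 mg to flag small LED changes. BKS response has no counterpart.

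**The concern.** A subject who receives more medication and whose bradykinesia score then rises is the clearest case of non-response. Under the written rule that subject is worsened rather than unchanged, and so is not counted. The subjects who are counted are those whose two medians happen to agree at the reported precision, which says more about rounding than about response.

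The neighbouring rates (uncontrolled subjects who became controlled, subjects unwilling to change treatment, subjects for whom a change was contraindicated) suggest a set meant to describe who improved and why others did not. In such a set, a low unresponsive rate could be taken as evidence that escalation usually moved BKS in the right direction, although the rule would return a low rate even if LED had no effect on BKS.

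**Working it through.** **Step 1: what the wording counts (no assumptions needed).** Take an illustrative subject with BKS 30 at baseline, an LED increase, and BKS 33 at 4 months. The change is 33 − 30 = +3, a deterioration under item 7. Against the four rates:

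- uncontrolled at baseline, then controlled: no, 33 is above 25;
- unresponsive: no, the score changed;
- unwilling to change treatment: no;
- contraindicated: no.

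The subject enters none of them. The SAP 3.5 ancillary rate of subjects not brought into target could include this subject only in PKG+, and it is not tied to an LED increase. The three-way change summary shows worsening without LED. Item 8 correlates LED change with 4-month BKS but counts nobody. No summary in the text counts worsening after an LED increase.

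**Step 2: how often a tie occurs (illustration).** The plan attaches no figure to this rate, so there is nothing to reproduce. Inputs, all assumed: BKS change is Normal with mean 0 (no effect of the LED increase) and SD 3, 4 or 5; change is reported to a precision r of 0.1 or 1 point.

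- Share unchanged = 2Φ(r / (2·SD)) − 1
- Share worsened = (1 − share unchanged) / 2

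For r = 1 and SD = 3: 2Φ(0.167) − 1 = 0.132, and (1 − 0.132) / 2 = 0.434.

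| Precision r | SD | Unchanged (counted) | Worsened (not counted) |
|---|---|---|---|
| 0.1 | 3 | 1.3% | 49.3% |
| 0.1 | 4 | 1.0% | 49.5% |
| 0.1 | 5 | 0.8% | 49.6% |
| 1 | 3 | 13.2% | 43.4% |
| 1 | 4 | 9.9% | 45.0% |
| 1 | 5 | 8.0% | 46.0% |

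So about 1% are counted at 0.1-point reporting and 8% to 13% at whole points, while 43% to 50% worsen and are left out.

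**Step 3: wider assumptions.** A simulation rounded both visit values (baseline mean 26, SD 4; 1,000,000 draws per scenario) and let the SD of change run from 2 to 6 and the mean change from 0 to −2.

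- At 0.1 precision: 0.6% to 2.0% tie and 15.2% to 49.7% worsen.
- At whole points: 6.3% to 19.5% tie and 10.8% to 46.8% worsen.

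A true mean improvement shrinks the omitted group but does not remove it.

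**Step 4: in this trial.** SAP 4.1 gives 41 enrolled subjects. If all 41 had an LED increase, which is the upper bound, the expected number of ties is 0.3 to 0.8 at 0.1 precision or 2.6 to 8.0 at whole points, both arms together.

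**Step 5: a zero cut-off alone is not enough.** Counting every change of 0 or above gives 50% to 57% unresponsive in the Step 2 scenarios (unchanged plus worsened). The remainder, including falls of 0.1, would still pass as response with no drug effect at all. Requiring a fall of at least 1 point would instead class 58.0% to 63.0% as unresponsive (SD 5 to 3, mean 0, unrounded).

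**The case against.** Several points can fairly be made for the plan.

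- **Precision is not stated.** The SAP writes its BKS targets and its worked example of BKS change in whole numbers. If the median is reported that way, ties are not rare. A reader might infer that almost nobody can qualify; the documents do not support that without knowing the precision. This stands. What remains is that the rate then depends on the reporting format.
- **Worsening is not hidden.** Items 2b and 7 report it in the continuous and categorical summaries. This stands, but neither crosses it with an LED increase.
- **The rest of the sample is never called responsive.** A reader might infer that the SAP will report near-universal response to escalation. It makes no such statement; the risk lies in how a low rate is read.
- **No purpose is stated.** A reader might infer that this rate decides how a null primary result is interpreted. Nothing in the documents says so, and other listed rates address that question more directly: uncontrolled subjects with no medication change, changes under 100 mg LED, and PKG+ subjects not brought into target.
- **The split by arm and control status is already in the stem.** This stands. The gap is narrower: subjects out of target include those who are dyskinetic only, for whom an unchanged BKS after an LED increase is not a failure to lower a raised score.
- **The authors may have meant no improvement, or the tables attachment (Appendix 2) may set limits.** Both are possible. The attachment is not part of the text available, and the SAP text itself does not say so.

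**Conclusion.** The point holds as a minor correction. That worsened subjects are excluded follows from the wording alone: item 7 equates unresponsive with no change and separates same from worsened by sign. The size is illustrative only. With mean change 0 and SD 3 to 5, the rule counts about 1% (0.1 precision) or 8% to 13% (whole points) and omits a further 43% to 50% who worsened. Those figures rest on an assumed distribution, SD and precision, none of which the documents give.

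The rate is one descriptive line under a secondary endpoint in a study that closed at 41 subjects. No hypothesis test, power figure or decision rule depends on it, and the primary analysis is unaffected.

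**What to change.** Replace the bracketed definition with an analysis rule along these lines:

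- Among subjects whose 4-month LED is above baseline LED (using item 8's convention that a change made at a visit counts from the next one), a subject is unresponsive if 4-month BKS is not lower than baseline BKS (change ≥ 0).
- Show unchanged and worsened subjects separately within that total, and state the precision at which BKS is analysed.
- Report by arm and by baseline control status. The main denominator is subjects with baseline BKS above 25 and an LED increase, so that subjects who are dyskinetic only do not enter it.
- As a sensitivity analysis, also count subjects whose BKS fell by less than a margin that the sponsor sets and justifies before analysis. The documents supply no such margin.

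If the tables attachment already holds limits for the categories, bring them into the SAP text and align the two.

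The cost is a short SAP edit and one extra table row or two from data already planned for the LED and PKG summaries. The reported unresponsive rate will be higher. The change concerns the analysis definition only and has no bearing on treatment.

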#### *Parkinson's Disease Medication Use*

All subjects in the study will be asked to continue taking Parkinson's disease medication(s) as prescribed by their Parkinson's clinician throughout the duration of this study. Any modifications to medicines made during this study will be based on the clinician's judgment. Changes to medications will be recommended until the patient is considered to be controlled

unless contraindications are identified by the investigator. All PD medications and subsequent changes will be recorded in the medication log CRF. In addition, non-PD prescription medications of anti-depressants, anti-psychotics and blood pressure lowering agents will be tracked in the other medication log CRF.

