#### 4.5 Interim Follow-Up Visits

Interim follow-ups will be completed for subjects who are not considered to be controlled. For PKG- group subjects, controlled means per clinician standard of care assessment and for PKG+ group subjects, this is per the Acceptable Target Range:

	Target Range
Bradykinesia Score (BKS)	Median BKS 23-25 and/or FDS > 7.5
Dyskinesia Score (DKS)	Median DKS 7-9 and FDS < 13

Interim visits can be completed in-clinic or remotely via telephone per institutional requirements. This timeframe may vary depending on a variety of factors such as physician care practices, amount of total medication change needed, subject medication regimen compliance and subject tolerance to medication changes.

Approximately 28 days prior to each planned subject follow-up visit, a PKG Watch will be ordered through the GKC Portal and dispensed to each subject as previously described and PKG report obtained prior to the visit of PKG+ group subjects for investigator review.

For subjects in the PKG+ Group, the site staff will ensure the PKG is available prior to the Interim Follow-up Visit. Protocol required data collection will occur at each follow-up interim visit. A Subject "ON" State Assessment will be completed and changes in medical history and medications will be recorded. Any protocol defined AEs that have occurred will be captured on the AE Reporting CRF (see Section 8). The study investigator will review the PKG provided by GKC prior to the visit and use the information to guide the discussion with the subject during the clinical assessment. PKG results will be recorded in the PKG Reporting CRF. The study investigator will complete the Clinician Assessment CRF to denote patient-reported symptoms, treatable findings, and clinical management planning based on his/her routine clinical assessment procedures along with the PKG information.

For subjects in the PKG- Group, protocol required data collection will occur at each follow-up interim visit. A Subject "ON" State Assessment will be completed and changes in medical history and medications will be recorded. The study investigator will complete the Clinician Assessment CRF to denote patient-reported symptoms, treatable findings, and clinical management planning based on his/her routine clinical assessment procedures. The study investigator will be blinded to the PKG information during interim visits.

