These steps will be repeated for each interim follow-up until the study subject is determined to be controlled or a maximum of the 4-month follow-up visit.

Up to 4 medication changes including at the Baseline visit and up to 3 interim visits will be allowed to get each subject into a “controlled” state. Interim follow-up visits end when PD symptoms have become optimized (considered controlled on oral therapies) per standard of care assessments for PKG- group subjects and per the Acceptable Target Range as published in Pahwa et al., 2018 and no further treatment changes are indicated as assessed by the study investigator and the subject will proceed to the next required study visit at 4-months Follow-Up.

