4.4. Study Assessments and Missing Data

In the event inaccurate and/or incomplete PKG data collection occurs (e.g., subject wore PKG successfully but for less than the required duration, subject PKG Watch was not sufficiently secured creating PKG artifacts precluding interpretation, subject performed activities, such as the use of power tools, for a sufficient duration that interfered with PKG data collection, data collection completed when subject was OFF), data collection may be repeated one time. A note will be made in the case report form (CRF) that documents the reason for the repeated data collection and the initial and final test results will be recorded in the medical record. Only the final results will be recorded on the CRF and used for analysis purposes. Techniques will not be used to impute missing data; evaluable data will be utilized.

Due to the impact of COVID-19 on ability to collect select data, notations have been made in the protocol deviation section of the data extract and will be provided as a summary categorization for analysis purposes.

Specifically, for the MDS-UPDRS Part III data was either:

- Completely collected for baseline and/or 4-months visit
- Partially collected for baseline and/or 4 months visit (i.e., rigidity (Q 3.3) and postural stability (Q3.12) questions not collected if a telehealth visit)
- Not collected for baseline and/or 4-month visit

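### Interim-visit LED and medication-change summaries cover only subjects still titrating under an arm-specific rule, so reading them by arm is not a randomised comparison

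*SAP*

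**What the plan says.** SAP 3.4 item 8 defines the endpoint as "Change in LED from baseline to each interim visit and 4 months". It plans "a comparison of change in LED at each visit for each patient" and also "Rate and change in PD medications including medication type, dosing, increase, decrease from baseline to interim1, interim2, interim3, and 4 months". By its timing rule, a change made at a scheduled visit is counted at the next visit.

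Protocol 4.5 decides who has an interim visit: "Interim follow-ups will be completed for subjects who are not considered to be controlled". The criterion differs by arm: "For PKG- group subjects, controlled means per clinician standard of care assessment and for PKG+ group subjects, this is per the Acceptable Target Range". It also sets the end: "These steps will be repeated for each interim follow-up until the study subject is determined to be controlled", or until the 4-month visit at the latest.

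On data that do not exist, SAP 4.4 says: "Techniques will not be used to impute missing data; evaluable data will be utilized".

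Three other provisions bear on the point:

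- Protocol 4.6 gives every subject a 4-month visit, whether or not interim visits took place.
- Protocol 4.2, under Parkinson's Disease Medication Use, says: "All PD medications and subsequent changes will be recorded in the medication log CRF". Protocol 4.6 has the log updated at 4 months.
- SAP 3.3 makes it a secondary objective to relate the frequency of medication changes to the PKG and clinical findings in participants with and without a PKG report available to the clinician.

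**The concern.** Having an interim visit is a post-randomisation event. In PKG+ it depends on the PKG target range, which is the intervention itself. In PKG- it depends on clinical judgement. The subjects who supply an interim-1 value are therefore chosen by different rules in the two arms, and the groups shrink by different rules at interims 2 and 3.

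The timing rule adds to this. A subject judged controlled at baseline, with no change made, has no interim 1, so that zero never enters the interim-1 summary. A subject controlled after interim 1 drops out of the interim-2 and interim-3 summaries, although the regimen reached is known.

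LED change is the trial's most direct evidence on whether PKG targets alter treatment. If the PKG works mainly by leading to changes in more subjects, summaries limited to those still titrating leave that effect out. If the arms differ in how severe the remaining subjects are, the summaries show a difference that the intervention did not cause.

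**Working it through.** The documents give no figure for this point, so there is none to reproduce. The first step follows from the documents. The other steps are illustrations.

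**1. Who is in each summary.**

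| Time point | PKG+ subjects with a visit | PKG- subjects with a visit |
|---|---|---|
| Interim 1 | out of PKG target at baseline | judged uncontrolled at baseline |
| Interims 2 and 3 | still out of target at the preceding visit | still judged uncontrolled at the preceding visit |
| 4 months | all | all |

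Item 7 (PKG scores) gives subjects without interim visits their own path, from baseline to 4 months. Item 8 has no such rule and does not say who enters each interim summary.

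**2. Inputs to the illustrations.** From the documents: 41 subjects (SAP 3.2 and 4.1), so 41/2 = 20.5 per arm at 1:1. Assumed:

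- p+ = 78% of PKG+ uncontrolled at baseline. The figure comes from the cohort cited in the Protocol Introduction, not from this trial.
- p- = 20% to 78% of PKG- uncontrolled.
- The LED amounts below.

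**3. A real difference hidden.** Assume the same mean LED change, d = 100 mg, in every uncontrolled subject of either arm, and 0 in the rest.

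- Attendees only: d - d = 100 - 100 = 0 mg, whatever p- is.
- All randomised: d × (p+ - p-).

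| p- | All randomised | Attendees only |
|---|---|---|
| 20% | 100 × 0.58 = 58 mg | 0 |
| 40% | 100 × 0.38 = 38 mg | 0 |
| 60% | 100 × 0.18 = 18 mg | 0 |
| 78% | 0 mg | 0 |

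**4. A false difference created.** Assume LED change has the same distribution in both arms (mean 100, SD 80 mg) and is driven by need. A share q attends, selected on need plus independent noise of equal variance, so the correlation with need is 1/√2 = 0.707. The mean among attendees is 100 + 80 × 0.707 × φ(z)/q, where z is the upper-q standard normal quantile and φ the normal density.

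- PKG+, q = 0.78: φ(z) = 0.2961, mean 121.5 mg.
- PKG-, q = 0.20: φ(z) = 0.2800, mean 179.2 mg; difference -57.7 mg.
- PKG-, q = 0.40: φ(z) = 0.3863, mean 154.6 mg; difference about -33 mg.
- PKG-, q = 0.60: φ(z) = 0.3863, mean 136.4 mg; difference about -15 mg.
- PKG-, q = 0.78: difference 0.

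The all-randomised difference is 0 throughout. A simulation with 200,000 subjects per arm gave -57.3, -32.9, -14.7 and 0.1 mg. The sign reverses if PKG- has the larger share attending.

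**5. Numbers attending.** Interim 1: 20.5 × 0.78 = 16.0 in PKG+. In PKG- it is 20.5 × 0.40 = 8.2, ranging from 4.1 at 20% to 16.0 at 78%. Assume that 25% to 50% of attendees become controlled at each visit. Interim 3 then has 16.0 × 0.75² = 9.0 down to 16.0 × 0.50² = 4.0 in PKG+, and 8.2 × 0.75² = 4.6 down to 8.2 × 0.50² = 2.1 in PKG- (p- = 40%).

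**The case against.** The strongest reply is that no interim comparison between arms is written. Item 8 speaks of each patient, which reads naturally as a within-patient summary, and names neither arm nor a test. Items 1, 7 and 9 do name the arms, and the opening of SAP 3.4 speaks of comparison between baseline and 4 months. This stands. A reader might infer that the SAP plans a biased interim test of LED; the documents do not support that. They support a narrower statement: the interim summaries lose comparability once they are read by arm, which the secondary objective in SAP 3.3 invites.

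A reader might also infer that the effect of the PKG on prescribing is lost altogether. It is not. Item 8 also covers change to 4 months, when every subject has a visit, and groups patients by number of medication changes through 4 months, with zero as a category.

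SAP 4.4 could be taken to forbid use of the regimen of subjects whose interim visits have ended. It addresses missing data. A regimen recorded in the log is observed, so using it is derivation and not imputation. Equally, item 8 does not say that such subjects are excluded; the programmer is left to choose.

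Finally, the milligram figures follow from what was assumed. The 78% describes a cohort with low access to specialist care, whereas this trial uses neurologists experienced in PD. That stands too: the figures show mechanism and direction, not a predicted bias.

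The reply does not remove the core. Summaries tied to visits that exist only for uncontrolled subjects, under arm-specific rules and with evaluable data only, give non-comparable subsets.

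**Conclusion.** The point holds as a minor one. The interim-visit summaries of LED and medication change condition on a post-randomisation event that is defined differently in each arm, and they should not be read as a randomised comparison. That conclusion rests on the visit rules alone.

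Its size cannot be derived from the documents. Under the stated assumptions, the attendee-only difference hides 18 to 58 mg or creates about 15 to 58 mg, for PKG- shares of 60% down to 20%. In these examples it is undistorted only when both arms have the same share uncontrolled. Small numbers, possibly 4 to 9 against 2 to 5 at interim 3, would limit interpretation further.

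The 4-month LED change, the count of medication changes through 4 months and the primary endpoint do not depend on who had interim visits. The 4-month results remain subject to ordinary dropout.

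**What to change.** In SAP 3.4 item 8:

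1. State that the between-arm comparison is LED change, and any medication change, from baseline to 4 months, PKG+ against PKG-, in all randomised subjects with data.
2. For earlier time points, derive LED from the medication log for every randomised subject at fixed nominal days after baseline, such as days 28 and 56. Subjects whose interim visits have ended contribute the regimen then in force. Day 84 is only 90 - 84 = 6 days before the 4-month window opens and would add little. Derive the rate of any medication change in the same way.
3. Keep the protocol-defined tables by interim visit, label them descriptive, and show the number attending in each arm.

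The sponsor should confirm that log entries are dated, which the documents do not state. Item 8's timing rule dates changes made at scheduled visits; changes made between visits need a recorded date.

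The cost is SAP wording, some extra programming, and one added derivation alongside the protocol's visit-based endpoint. If the log entries are dated, no new data are needed.
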